**Study Visit 3 (week 12 +/- 2 Weeks):**

- Participants will return to the hospital. They should wear clothing that is comfortable for them while you may be participating in physical activity. Study members will offer specific guidance on study if necessary. The following procedures will be performed during this visit with their test Socket B following 6 weeks of use.
- **TEWL measurement**

- **Laser Speckle Flowmetry (LSI)**
- **In-Socket Sensors**
- **Motion Capture Analyses**
- **6 Minute Walk Test (6MWT)**
- **Timed Up-and-Go (TUG)**
- **Houghton Scale**
- **Socket Comfort Score**
- **Veterans RAND 36-Item Health Survey**

**Study procedure details.**

- **Baseline TEWL measurement:** Small non-invasive probe that compares relative humidity of skin surface to indicate epidermal barrier functioning. The TEWL probe will be placed on the skin and each measurement takes approximately 7-20 seconds to obtain. An additional reference (control) TEWL measurement will be taken from intact skin at the anatomically matched site on the patient's contralateral side. TEWL measurements will be captured 3 times on the anterior, lateral, medial, and posterior surfaces on both limbs.
- **Laser Speckle Flowmetry (LSI):** LSI is a non-invasive blood flow imaging technique. LSI is very routinely used for blood perfusion measurement in clinical applications. We do not anticipate any radiation exposure.
- **Pressure Socket Sensors:** In-socket sensors will be positioned into the socket which will function to detect the amount of residual load (pressure) that is placed on the limb through the use of an iPad under a dynamic environment. This research functions to better understand the participant's in-socket pressure in a non-weight bearing socket compared to the Symphonie Aqua Digital System (SADS) system.
- **Motion Capture Analyses** Initiation of the in-socket sensors will ensue and walking tasks will be completed by subjects.
- **6 Minute Walk Test (6MWT):** Subject will walk for 6 consecutive minutes and, once the 6 minutes has elapsed, the distance covered will be measured. The reliability and/or concurrent validity of this assessment have been verified and reported in subjects with lower-limb amputations.
- **Timed Up-and-Go (TUG):** In the timed up-and-go outcome, the patient rises from a seated position, walks three meters at a self-selected speed, turns around, and returns to the chair where they reseat themselves. This measure is simply a timed event with the clinician timing from the moment the patient leaves the chair until they are reseated. Again, the reliability and/or concurrent validity of this assessment have been verified and reported in subjects with lower-limb amputations.

- **Houghton Scale:** A score of nine or more defined as successful prosthetic rehabilitation.
- **Socket Comfort Score:** This score is a subjective measure of how comfortable the amputee feels in the socket at the time the score is taken.
- **Veterans RAND 36-Item Health Survey:** Is a brief, generic, multi-use, self-administered health survey comprised of 36 items. The instrument is primarily used to measure health-related quality of life, to estimate disease burden and to evaluate disease-specific impact on general and selected populations.
- The fitting procedures and/or techniques of the research socket will mirror the techniques of the subject's primary prosthetist used to fabricate their SOC socket. The only difference is the method of capturing the shape of the residual limb: weight-bearing vs non-weight-bearing.
- There may be risks that we don't know about at this time. While the goal of this project is to create a more comfortable prosthesis, it is possible that subjects will experience discomfort such as perspiration, dry skin, rash, itching, irritation, blisters, high pressure in the socket, looseness in the socket, and mechanical rubbing which may cause ulcerations.

## 6.0 Study Calendar

	Study Visit 1 (0-6 weeks)	Study Visit 2 (6+/- 2 Weeks)	Study Visit 3 (12+/- 2 Weeks)
Informed consent 	X		
Enrollment	X		
Socket Shape capture	X		
Initial Evaluation/fitting	X		
TEWL measurement	X	X	X
Laser Speckle Imaging (LSI)	X	X	X
Pressure Socket Sensors	X	X	X
Motion Capture Analysis	X	X	X
6-minute Walk Test	X	X	X
Timed UP and GO	X	X	X
Houghton Scale	X	X	X
Socket Comfort Score	X	X	X
Veterans RAND36-item health survey	X	X	X

## **7.0 Reportable Events**

Protocol deviations and Unanticipated Problems involving risks to subjects or others, Adverse Events, and Other Problems will be reported to Indiana University per IU IRB reporting requirements.

Unanticipated problems can occur in any type of research (medical or non-medical) and may include occurrences such as adverse events, subject complaints, protocol deviations, and other untoward events involving risk. Events requiring prompt reporting by investigators and research staff may involve physical, psychological, social, legal, or economic harms.

Event reports and accompanying information will be screened for completeness by research staff members, additional clarifications will be requested from the investigator, as necessary. Research staff members and the principal investigator will make an initial determination about whether the event represents a possible unanticipated problem involving risks to subjects or others and/or potential noncompliance. Reports of events determined during screening to represent possible unanticipated problems involving risks to subjects or others and/or serious/continuing noncompliance will be forwarded to the IRB for convened review. Reports of events that do not meet the requirements for prompt reporting may be reported at time of study renewal.

## **8.0 Data Safety Monitoring**

A clinician/certified prosthodontist who is a member of the study team and the study coordinator will meet at the following timepoints to review the study data and any adverse events to ensure continued subject safety: prior to initiation of the study, after the 5th subject is enrolled, after the 10th subject is enrolled, and 60 days following the conclusion of study procedures for all subjects. Data will be reviewed at least annually.

## **9.0 Study Withdrawal/Discontinuation**

Patients will be informed during the informed consent process (in writing and verbally) that they are free to withdraw from the trial at any time. The investigator may exercise his medical judgement to terminate a patient's participation in the trial due to clinically relevant changes in any clinical or laboratory parameter. The Sponsor-Investigator also reserves the right to discontinue/terminate the trial at any time.

Discontinuation criteria for individual subjects include: (1) Non-compliance with the inclusion/exclusion criteria, (2) treatment non-compliance, such as use of another socket prosthesis, (3) withdrawal from the study due to reasons not related to the treatment, (4) prosthetic socket becomes uncomfortable.

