Achieving a comfortable and functional relationship between an amputee and their prosthetic socket is critical to the success of the prosthesis. Therefore, the prosthetic socket and interface are the most significant component for the overall rehabilitative success of the prosthesis. Over 75% of patients with lower-limb prosthetics have skin problems. Ulcers or pressure sores, are the most common skin conditions in prosthetic users and can vary in size and magnitude requiring prolonged recovery time out of the prosthesis, a new socket fitting and sometimes surgical interventions. To preserve and promote residual limb health, one key factor is to maintain the functional integrity of the skin, perfusion and oxygenation. Functional integrity of the skin is a critical determinant of ulcer formation. Our group and others have demonstrated that trans-epidermal water loss (TEWL) measures the functional integrity of the skin, a reliable early marker of skin ulceration. Breach in physical integrity of the skin is preceded by breach of functional integrity of skin as measured by elevated TEWL. Previous research lends credence to the hypothesis that the residual limb skin is susceptible to breakdown and ulceration in response to repeated stress from use of prosthesis.

Micro-vasculopathy is known to complicate limb health. We reported the first post-processing of binary raw data from a high-resolution LSCI camera. This tool is valuable in determining micro-vasculopathies compromising limb health following use of a specific type of socket. These studies described above clearly demonstrate value of in-socket and out-of-socket non-invasive unique measurement tools developed by our group for monitoring limb health of residual limb in sockets. These studies also demonstrate experience of our group in performing such clinical studies in this area.

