#### **5.2 Study Procedures**

**Study Visit 1a-c (Initial Evaluation/Fitting; Weeks 0-6):** Immediately post-enrollment, socket shape capture will be completed with Digital and non-digital weight bearing Aqua systems. Baseline measurement for SoC will be performed. The following baseline measurements will be performed for SoC Socket (Socket A) at this first visit:

- TEWL measurement
- Laser Speckle Flowmetry (LSI)
- In-Socket Sensors
- Motion Capture Analyses
- 6 Minute Walk Test (6MWT)
- Timed Up-and-Go (TUG)
- Houghton Scale

- **Socket Comfort Score**
- **Veterans RAND 36-Item Health Survey**

The fitting of the digital and non-digital weight bearing sockets will continue for up to 4-6 weeks to ensure proper fitting of the weight bearing socket and comfortability during this time the subjects will continue to use their SoC socket A.

**Study Visit 2 – SoC final visit (week 6 +/- 2 Weeks):** Participants will return to the hospital. Participants will be asked to wear clothing that is comfortable for them while they may be participating in physical activity prior to attending the visit. Study members will offer specific guidance on study if necessary. If they do not have any comfortable clothing, they will be asked to speak with research personnel. Research personnel will provide them with the appropriate clothing if they are unable to bring any during this visit. The following procedures will be performed during this visit with their Socket B.

- **TEWL measurement**
- **Laser Speckle Flowmetry (LSI)**
- **In-Socket Sensors**
- **Motion Capture Analyses**
- **6 Minute Walk Test (6MWT)**
- **Timed Up-and-Go (TUG)**
- **Houghton Scale**
- **Socket Comfort Score**
- **Veterans RAND 36-Item Health Survey**

At this visit, the definitive **socket B** will be ready & fitted; the measurements in this visit will serve **as the baseline visit values for Socket B**; End of this visit the participants will start using the Socket B for next 6 weeks Study members will offer specific guidance on study as necessary.

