## **10.0 Statistical Considerations**

This is a pilot study that is expected to generate preliminary data that will inform sample size for an adequately powered phase 2 study (in future). In this study, a total of n=12 subjects will be enrolled.

In general, for continuous data, means, median, standard deviations, and range will be provided. For categorical data, the count and frequency will be provided. In general, inferential tests will be tested with two-sided p-values or 95% confidence intervals, unless otherwise stated. Missing data distributions and patterns will be checked, and in the scenario of missing at random (MAR), we will consider multiple imputation procedures in data analysis. For Aim 1, TEWL values will be used as a function of overall limb health and as our primary endpoint. In addition to the primary endpoint, the secondary endpoint Laser Speckle Imaging will also be examined in aim 1. All of these endpoints are measured or quantified into continuous scale that would be used as outcomes. For Aim 2, functional outcomes will be evaluated using 2MWT and TUG, at baseline and at 6 weeks period post-socket use. To test the hypothesis, all these functional measurements will be transformed into standardized Z-scores with mean of 0 and a standard deviation of 1. These standardized scores will then be pooled into one composite score to quantify standardized functional score. The patient reported outcomes (PRO) will be assessed using validated instruments: Summary measures will be derived by summation of item specific scores for each instrument. These summary measures from functional measures and PRO will then be transformed into standardized Z-scores to create a pooled (composite) score for the overall PRO. For functional and PRO measure, generalized linear mixed methods with carryover effect, if any, will be used to examine the effect of types of socket on composite measure of the measures. A profile plot of the mean (or median) of each continuous endpoint variable will be created over follow-up time for each arm of the test-socket. All analyses will be done using SAS 9.4 or Stata 16.0 or higher.

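### Stopping for socket discomfort takes a subject out of the study before the only assessment after Socket B use, and the analysis plan has no rule that brings the stop into the socket comparison

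*Combined protocol and SAP*

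**What the plan says.** Section 9.0 opens with the subject's freedom to withdraw from the trial and the investigator's right to end participation. It then lists discontinuation criteria for individual subjects. Criterion (4) is "prosthetic socket becomes uncomfortable" and criterion (2) is "treatment non-compliance, such as use of another socket prosthesis". Neither is limited to one socket.

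Under Sections 5.1 and 5.2 everyone uses Socket A (standard of care) first. Socket B is fitted at Visit 2 (week 6 ± 2), the values taken there serve "as the baseline visit values for Socket B", and Socket B use starts at the end of that visit. Visit 3 (week 12 ± 2) is done "with their test Socket B following 6 weeks of use". The study calendar has three visits and no measurement at early stopping.

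Section 10.0 names TEWL as the primary endpoint. On missing data it says: "Missing data distributions and patterns will be checked, and in the scenario of missing at random (MAR), we will consider multiple imputation procedures". It defines no analysis population, no failure rule and no sensitivity analysis for data that are not missing at random.

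**The concern.** The reason for leaving is itself something the trial measures. The Socket Comfort Score is taken at every visit, and Section 5.2 describes it thus: "This score is a subjective measure of how comfortable the amputee feels in the socket at the time the score is taken". A link with the primary endpoint is plausible on the protocol's own reasoning. Section 5.2 warns of "high pressure in the socket, looseness in the socket, and mechanical rubbing which may cause ulcerations", and Section 1.0 states: "Breach in physical integrity of the skin is preceded by breach of functional integrity of skin as measured by elevated TEWL". A subject whose new socket rubs or presses may therefore be one whose TEWL is rising.

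Section 5.0 sets the comparison after six weeks of use, so the value lost is the one the comparison rests on. The pilot is also meant to inform the sample size of a phase 2 study. Planning that study needs the proportion who stop Socket B for discomfort as well as the outcome in those who continue.

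**Working it through.** **What happens to a subject who cannot tolerate Socket B**

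1. Socket B use begins at the end of Visit 2. That visit's Socket B values come from the fitting day and cannot show later intolerance.
2. If discomfort develops between weeks 6 and 12, criterion (4) applies. If the subject goes back to Socket A, criterion (2) applies as well.
3. No visit falls between Visit 2 and Visit 3, and none is triggered by stopping. No 6-week Socket B value is obtained.
4. An imputation under MAR would draw on the subject's Visit 1 and 2 values and on the Visit 3 values of those who continued. No scheduled measurement captures the discomfort, so the imputed value would tend to resemble a continuer's.

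**Size**

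The plan has no dropout rate, SD or effect size, so there is no figure of its own to reproduce. Only n = 12 comes from the documents. The numbers of stops, the correlations and normality are assumptions.

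*Chance of at least one discomfort stop*, 1 − (1 − p)^12: 46% at p = 5%, 72% at 10%, 93% at 20%, 99% at 30%.

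*Still using Socket B* (exact Clopper-Pearson 95% CI) *and expected shift in the Visit 3 mean*. For the shift, assume that the k subjects who stop are exactly those with the worst Visit 3 values. The expected sizes of the three most extreme of 12 standard normal values are 1.629, 1.115 and 0.792. The expected shift is the sum of the first k divided by (12 − k). The last column fills in the missing values by regression on Visit 2, with an assumed correlation of 0.5 (100,000 simulated samples).

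| Stops k | Still using (95% CI) | Expected shift, continuers only | Expected shift after imputation |
|---|---|---|---|
| 0 | 12/12 = 100% (74 to 100%) | 0 | 0 |
| 1 | 11/12 = 92% (62 to 99.8%) | 1.629/11 = 0.15 SD | 0.12 SD |
| 2 | 10/12 = 83% (52 to 98%) | 2.744/10 = 0.27 SD | 0.22 SD |
| 3 | 9/12 = 75% (43 to 95%) | 3.536/9 = 0.39 SD | 0.33 SD |

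With a correlation of 0.3 the shifts left after imputation are 0.14, 0.26 and 0.37 SD; with 0.7 they are 0.08, 0.17 and 0.25 SD.

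These are averages over repeated studies under extreme selection, not limits. In a single study of 12 under the same selection, the 95th percentiles of the shift among continuers are about 0.23, 0.40 and 0.56 SD.

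*Within-subject comparison under milder selection.* Simulate 12 differences (B minus A) with no true effect. Remove the k subjects with the worst discomfort, where discomfort has correlation r with the difference, and run a two-sided 5% paired t-test on the rest (40,000 runs). The nominal rate of a false finding for B is 2.5%.

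| r | k = 1 | k = 2 | k = 3 |
|---|---|---|---|
| 0 | no shift, 2.6% | no shift, 2.6% | no shift, 2.4% |
| 0.3 | 0.04 SD, 3.4% | 0.08 SD, 4.4% | 0.12 SD, 5.2% |
| 0.5 | 0.08 SD, 4.3% | 0.14 SD, 6.5% | 0.20 SD, 8.3% |
| 0.8 | 0.12 SD, 6.4% | 0.22 SD, 11.7% | 0.31 SD, 17.8% |

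The shift is towards Socket B when r is positive, and absent when discomfort is unrelated to the outcome.

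**The case against.** The strongest reply is that the plan never says leavers are excluded. Section 9.0 does not say how uncomfortable a socket must be, whether adjustment is tried first, or that a last measurement is barred. The mixed model for Aim 2 can keep Visit 1 and 2 data. That stands: a reader might infer that discomfort stops are deliberately dropped from the analysis, and the documents do not support that. What they show is the absence of any rule that brings such stops into the comparison.

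The number of stops may also be small. Section 5.2 allows up to 4-6 weeks of fitting before Socket B is definitive, and Section 14.0 describes a refitting feature. Both may lower the number, but neither removes the rule.

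Discomfort stops would not be invisible either. Adverse events are reported and reviewed (Sections 7.0 and 8.0), missing data are monitored (Section 11.0), and Section 10.0 promises counts for categorical data in general. These provisions would probably reveal a stop, but they do not bring it into the socket comparison.

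Allowing a subject to stop for discomfort is proper protection and is not in question. Criterion (4) also covers Socket A. However, Socket A is the subject's existing socket and always comes first, so the new socket's 6-week result is the more exposed.

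**Conclusion.** The point holds as a weakness in a stated rule, and it should be changed. If Section 9.0 is followed on its natural reading, the Visit 3 Socket B result is conditional on having stayed comfortable enough to continue, and possible imputation under MAR does not reliably repair that. The direction favours Socket B if discomfort goes with worse outcomes. The protocol's text makes that plausible but does not establish it.

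The number of stops and the size of any bias are unknown. A reader might take the SD figures above as the bias in this trial or as its upper bound. They are neither, because they rest on assumed numbers of stops, normality and assumed selection. With no stops there is no effect, but with 12 subjects each stop removes 1/12, or 8%, of the sample.

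**What to change.** **Section 9.0.** Make criteria (4) and (2) reasons to stop the socket, not to leave the study; subjects stay free to withdraw altogether. Record the date, the socket and the reason. Where safe and agreed, take at least TEWL and the Socket Comfort Score at the contact when Socket B is stopped, and label them as Socket B. Treat any later visit on Socket A as follow-up: a value taken weeks after going back is not a Socket B outcome.

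**Section 10.0.** Over all 12 enrolled, report the number fitted with a definitive Socket B and the number still using it at Visit 3 (exact 95% CI), with reasons. State that Visit 3 Socket B results are conditional on continued use. Add one sensitivity analysis that gives discomfort stops an unfavourable Socket B value, for example the worst rank. Without it, the counts and the caveat would leave the TEWL comparison restricted to continuers.

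**Cost.** A few sentences, a few data fields if the case report forms lack them, and possibly a brief extra contact for those who stop. No added subjects are needed. The headline result may look less favourable, because discomfort stops become part of it.

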## **10.0 Statistical Considerations**

This is a pilot study that is expected to generate preliminary data that will inform sample size for an adequately powered phase 2 study (in future). In this study, a total of n=12 subjects will be enrolled.

In general, for continuous data, means, median, standard deviations, and range will be provided. For categorical data, the count and frequency will be provided. In general, inferential tests will be tested with two-sided p-values or 95% confidence intervals, unless otherwise stated. Missing data distributions and patterns will be checked, and in the scenario of missing at random (MAR), we will consider multiple imputation procedures in data analysis. For Aim 1, TEWL values will be used as a function of overall limb health and as our primary endpoint. In addition to the primary endpoint, the secondary endpoint Laser Speckle Imaging will also be examined in aim 1. All of these endpoints are measured or quantified into continuous scale that would be used as outcomes. For Aim 2, functional outcomes will be evaluated using 2MWT and TUG, at baseline and at 6 weeks period post-socket use. To test the hypothesis, all these functional measurements will be transformed into standardized Z-scores with mean of 0 and a standard deviation of 1. These standardized scores will then be pooled into one composite score to quantify standardized functional score. The patient reported outcomes (PRO) will be assessed using validated instruments: Summary measures will be derived by summation of item specific scores for each instrument. These summary measures from functional measures and PRO will then be transformed into standardized Z-scores to create a pooled (composite) score for the overall PRO. For functional and PRO measure, generalized linear mixed methods with carryover effect, if any, will be used to examine the effect of types of socket on composite measure of the measures. A profile plot of the mean (or median) of each continuous endpoint variable will be created over follow-up time for each arm of the test-socket. All analyses will be done using SAS 9.4 or Stata 16.0 or higher.

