## **2.2 Secondary Objective**

The secondary objective includes

- i) pressure inside the socket
- ii) assessment of functional outcomes
- iii) patient reported (PR) outcomes

We hypothesize that digital shape capture of a residual limb using EMTS under full weight bearing environment will provide accurate anatomical shape of the residual limb, improved fit of the prosthetic socket; thus, preserving limb health and volume during activities of daily living (ADL). Such accuracy will improve limb health and rehabilitation outcomes following amputation.

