### **3.2 Aim 2**

Long-term assessment of functional outcomes, and patient reported (PR) outcomes in response to use of SADS.

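### As written, the overall PRO composite takes in functional measures that already have their own composite, so the modelled score mixes performance tests with self-report

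*Combined protocol and SAP*

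**What the plan says.** Section 2.2 lists functional outcomes as secondary objective ii and, as a separate item, "iii) patient reported (PR) outcomes". Aim 2 (Section 3.2) also names both: "Long-term assessment of functional outcomes, and patient reported (PR) outcomes in response to use of SADS".

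Section 10.0 then defines the Aim 2 scores in this order:

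- The functional tests are named: "For Aim 2, functional outcomes will be evaluated using 2MWT and TUG, at baseline and at 6 weeks period post-socket use".
- They are standardized: "all these functional measurements will be transformed into standardized Z-scores with mean of 0 and a standard deviation of 1".
- They are pooled: "These standardized scores will then be pooled into one composite score to quantify standardized functional score".
- Each PRO instrument is totalled: "Summary measures will be derived by summation of item specific scores for each instrument".
- The second composite is formed: "These summary measures from functional measures and PRO will then be transformed into standardized Z-scores to create a pooled (composite) score for the overall PRO".
- The model follows: "For functional and PRO measure, generalized linear mixed methods with carryover effect, if any, will be used to examine the effect of types of socket".

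Section 10.0 does not name the PRO instruments, give component weights, or say in which direction each component is scored. Section 5.2 describes the walk test as a measured distance and TUG as a time taken by the clinician.

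**The concern.** The sentence that forms the second composite names functional measures as an input to a score labelled PRO. Those measures have just been pooled into a score of their own. A programmer who follows the text would put the walk test and TUG into both Aim 2 composites.

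Three things would follow. A socket effect on walking alone could register as patient-reported benefit. A real change in comfort or quality of life would be diluted by tests that did not move. And the two Aim 2 results would be correlated by construction, so agreement between them would be weaker support than it looks. The study is meant to inform the sample size of a later trial. If the PRO composite is used for that, its effect size and SD would partly reflect walking performance.

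**Working it through.** The documents give no effect size, SD, weight or power for these composites, so there is no figure to reproduce. The text is compared first; the sizes after it are illustrations.

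**Text.** Sections 2.2 and 3.2 keep function and PRO apart. Section 10.0 keeps them apart for the functional composite and joins them for the PRO composite. No other section gives a PRO-only composite or lists its components.

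**Assumptions.** Equal weights. Two functional tests (Section 10.0). Three PRO instruments, inferred from Section 5.2: Houghton Scale, Socket Comfort Score, VR-36. Unit-variance z-scores with a common correlation r of 0.3 to 0.5. A common positive r presumes that TUG is oriented so that higher is better.

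**Weight of the functional tests.** Entered separately: 2/5 = 40%. Entered as one re-standardized term: 1/4 = 25%.

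**SD of a mean of k z-scores:** sqrt((1 + (k−1)r)/k).

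| k | r = 0.3 | r = 0.5 |
|---|---|---|
| 3 (PRO only) | 0.730 | 0.816 |
| 4 | 0.689 | 0.791 |
| 5 | 0.663 | 0.775 |

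**Dilution.** Each PRO improves by 0.5 and function does not change.

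- PRO-only score: shift 0.5; 0.5/0.730 = 0.68 and 0.5/0.816 = 0.61 composite SDs.
- Five components: shift 0.5 × 3/5 = 0.30; 0.30/0.663 = 0.45 and 0.30/0.775 = 0.39. From unrounded values the loss is 34% and 37%.
- Four components: shift 0.5 × 3/4 = 0.375; 0.375/0.689 = 0.54 and 0.375/0.791 = 0.47. The loss is 21% and 23%.

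In raw z units the losses are 40% and 25%. They are smaller in composite-SD units because adding components also reduces the SD.

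**Contamination.** Function improves by 0.5 SD (each test when they enter separately, the functional term when it enters as one) and no PRO changes.

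- Five components: 0.5 × 0.40 = 0.20; 0.20/0.663 = 0.30 and 0.20/0.775 = 0.26 SDs.
- Four components: 0.5 × 0.25 = 0.125; 0.125/0.689 = 0.18 and 0.125/0.791 = 0.16 SDs.

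**If TUG is not re-oriented.** Equal 0.5 SD gains in both tests enter as +0.5 and −0.5, and the spurious shift is 0. The dilution also shrinks. With TUG correlated −r with every other component, the five-component SD is sqrt(5 + 4r)/5 = 0.498 and 0.529, so 0.30 becomes 0.60 and 0.57 SDs, a loss of 12% and 7%. With four components the functional term is uncorrelated with the PROs and the SD is sqrt(4 + 6r)/4 = 0.602 and 0.661, so 0.375 becomes 0.62 and 0.57, a loss of 9% and 7%.

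**Built-in correlation of the two composites.** Let F be the sum of the two functional z-scores and P the sum of the three PRO z-scores.

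- All components uncorrelated: sqrt(2/5) = 0.63 (tests separate) or sqrt(1/4) = 0.50 (one term), against 0 for a PRO-only score. With two to four PRO instruments the ranges are 0.71 to 0.58 and 0.58 to 0.45.
- Correlation 0.5 within domains and 0.3 across: Var F = 3, Var P = 6, Cov(F,P) = 2 × 3 × 0.3 = 1.8. A PRO-only score gives 1.8/sqrt(3 × 6) = 0.42. With the tests separate: (3 + 1.8)/sqrt(3 × 12.6) = 0.78. With one term, F/sqrt(3) has covariance 1.8/sqrt(3) = 1.039 with P, giving (1 + 1.039)/sqrt(1 + 6 + 2 × 1.039) = 0.68.

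**The case against.** The strongest reply is that the sentence is loose drafting. The authors may have meant two parallel composites, which the separate listing in Sections 2.2 and 3.2 and the opening of the model sentence both favour. Or they may have meant one combined Aim 2 score with the wrong label. This stands as a reason not to treat the literal reading as the certain intention. It does not remove the point, because each of these readings requires the sentence to be rewritten and nothing elsewhere settles the choice.

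A reader might infer that the PRO objective cannot be answered at all. The documents do not support that. Section 10.0 plans descriptive summaries of continuous data and a profile plot of each continuous endpoint, so the individual instruments may be seen separately. What is affected is the composite that goes into the model.

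A reader might also take both functional tests to be timed by the clinician. Section 5.2 says so only for TUG; the walk test records distance. Neither is described as self-report, and that is enough for this point.

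The sizes are open to challenge, rightly. Section 10.0 names no instruments, Section 5.2 does not say whether the Houghton Scale is patient-reported or functional, and no sign rule for TUG is given. The figures are therefore illustrations. Some correlation between the composites would also remain in a clean design (0.42 in the example above), and the plan nowhere presents the two results as independent support.

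**Conclusion.** The point holds as a defect in the written definition. Followed literally, Section 10.0 gives a PRO composite that mixes performance tests with self-report, weakens a true PRO effect and overlaps the functional composite.

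Under the stated assumptions, including an oriented TUG, a PRO-only effect loses about a third of its standardized size if the tests enter separately and about a fifth if they enter as one term. A functional gain of 0.5 SD would show as at most 0.30 SD of apparent PRO benefit. Without orientation of TUG both effects are smaller, and the apparent benefit can vanish. The overlap in content remains either way.

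The consequences are modest. These are Aim 2 secondary outcomes in a pilot of 12 subjects, the TEWL primary endpoint is untouched, and no stated alpha or power depends on the composites. The sentence should be corrected before analysis, so that the choice among readings is not made after the data are seen.

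**What to change.** Reword the sentence in Section 10.0 along these lines: *The PRO composite is formed from the standardized summary scores of the patient-reported instruments only, namely [list]. The functional tests enter the functional composite only.* The sponsor should name the instruments. Section 5.2 suggests the Houghton Scale, Socket Comfort Score and VR-36, to be confirmed. Add that each instrument's socket comparison will be reported on its own scale beside the composite.

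This costs one or two sentences and a small programming change, and needs no new data. The downside is that the PRO composite has fewer components.
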